Levels of circulating inflammatory cytokines. We will monitor the impact of Tofacitinib on cytokines using multiplex immunoassays with Meso Scale Discovery (MSD) technology, which are highly efficient sandwich immunoassays used to measure the levels of multiple protein targets within a single, small-volume reaction. MSD utilizes electrochemiluminescence to detect multiple binding events simultaneously with patterned arrays. We will use a custom V-PLEX platform following standard manufacturers' protocols as in our recent publication (28). This panel consists of cytokines that are significantly elevated in people with DS, with obvious ties to IFN signaling, autoimmunity in general, and immune skin conditions in particular (*Figure 4* and data not shown). We will measure multiple cytokines, chemokines, and immune factors dysregulated in DS, including but not restricted to: IP10, TNF α , CRP, IL6, IL10, MCP1, IL2, IL22, VEGF, IL17A, IL8, MIP1 α , IL29 (IFN λ), IFN γ , and IL1 β . Four of these cytokines (IP10, TNF α , CRP, IL6) will be used to create a composite Z-score (*Figure 4B*) to be used in endpoint evaluation, with the other cytokines being measured for research purposes. To minimize batch effects, we will use the V-PLEX immunoassays, which are analytically validated with guaranteed performance specifications that offer consistent results over long-term studies. Each assay employs a maximum volume of 25 μ L and each plasma sample is analyzed in duplicate. Plates will be read on the Meso QuickPlex SQ 120 system and data analyzed using the MSD workbench software. Absolute quantifications are determined with MSD-provided standards. We define success of this endpoint as statistically significant reduction in the cytokine score at 16 weeks of treatment as defined by two-sided, paired Student's t-test.

Levels of neurotoxic metabolites in the IFN-inducible kynurene pathway. Plasma metabolomics will be performed at the Metabolomics Core at CU-Anschutz using established protocols and instruments as

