Method: This number is based on published safety data for Tofacitinib for the treatment of rheumatoid arthritis in the general population, which indicates a rate of 9.4 SAEs per 100 patient years. Given that our trial aims to enroll 47 participants for 16 weeks of treatment (though we anticipate up to seven participants would be lost to attrition at various times during the treatment course) for a maximum total of 14.5 patient years of treatment, a comparable number of SAEs is 1.36.

Specific Aim 2. To determine the impact of JAK inhibition on the immune dysregulation caused by trisomy 21.

The overall goal of our data analysis plan in this Aim is to define which immune processes dysregulated by T21 can be normalized by Tofacitinib treatment, i.e. returned to values observed in typical people. Importantly, data shown in this proposal demonstrate that we have already defined the directionality and average magnitude of the change between people with and without T21. For example, we determined that IFN scores are significantly higher in people with DS (*Figure 3C*) and expect that Tofacitinib will reduce these values. Whereas some of the features dysregulated by T21 may be normalized by Tofacitinib treatment, others may not, and this will provide an important mechanistic insight to understand the molecular underpinnings of immune dysregulation in DS. Accordingly, the endpoints associated with this Specific Aim focus on effects of Tofacitinib (16 weeks of treatment) on four classes of molecular markers of immune dysregulation:

Primary Endpoint: Change in IFN scores in the transcriptome of white blood cells.

Endpoint Definition: Statistically significant reduction in average IFN scores between baseline and 16 weeks as defined by a two-sided, paired Student's t-test.

Method: To determine the impact of Tofacitinib on IFN scores, a two-sided, paired Student's t-test will be used to compare baseline and 16 weeks of treatment for participants with good compliance with the study drug (2 or fewer missed pills) and without a confounding reported adverse event in the 7 days prior to the Visit 7 endpoint. With 40 participants, we have 80% power to detect an effect size of 0.45 with a p-value <0.05, as calculated by G*Power software.

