Exploratory Research Goal: A more exploratory research goal, not considered part of the primary endpoint, would be to define if there are differences in IFN scores between clinical 'responders' and 'non-responders' as defined by changes in IGA, DLQI, or skin-specific scores as defined in Specific Aim 3 below. It is difficult at this point to estimate how many responders versus non-responders there will be in the study, and hopefully, all participants will see clinical improvement, in which case this exercise will not be necessary. Assuming that half of the participants will see clinical improvement as defined by IGA for example (i.e. 20 responders versus 20 non-responders), we are powered to see an effect size of 0.66 between the two groups.

Secondary Endpoint: Change in levels of circulating cytokines.

Endpoint Definition: Statistically significant reduction in the cytokine score at 16 weeks of treatment as defined by two-sided, paired Student's t-test.

Method: To determine the impact of Tofacitinib treatment on the Cytokine Score values (a composite Z score derived from the measurements of IP10, TNF- α , CRP, and IL6), a two-sided, paired Student's t-test will be used to compare baseline and 16 weeks of treatment for participants with good compliance with the study drug (2 or fewer missed pills) and without a confounding reported adverse event in the 7 days prior to the Visit 7 endpoint. With 40 participants, we have 80% power to detect an effect size of 0.45 with a p-value less than 0.05, as calculated by G*Power software.

Exploratory Research Goals: For an exploratory component of this analysis to test the impact of Tofacitinib on individual plasma cytokine levels (15+ cytokines measured in total, see *Research Strategy*), using a non-parametric Kolmogorov-Smirnoff (KS) test with 40 participants comparing baseline and 16 weeks of treatment, we have 80% power to detect an effect size of 0.47 with a p-value <0.05, as calculated by G*Power software, using FDR correction for multiple testing on 15 cytokines. This investigation will include cytokines isolated from both the blood and non-invasive skin tapes. For the exploratory goal of defining differences between responders and non-responders, assuming that half of the participants will see clinical improvement, we are powered to see an effect size of 0.66 for the composite Cytokine Score and 0.68 for individual cytokines.

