Tertiary Endpoint: Change in levels of neurotoxic metabolites in the kynurene pathway.

Endpoint Definition: Statistically significant reduction in one or more of three kynurenone dysregulation values at 16 weeks of treatment as defined by a two-sided, paired Student's t-test with FDR correction.

Method: To determine the impact of Tofacitinib treatment on the levels of kynurenone, quinolinic acid, and the kynurenone/tryptophan ratio, a two-sided, paired Student's t-test will be used to compare baseline and 16 weeks of treatment for participants with good compliance with the study drug (2 or fewer missed pills) and without a confounding reported adverse event in the 7 days prior to the Visit 7 endpoint. With 40 participants, we have 80% power to detect an effect size of 0.45 with a p-value less than 0.05, as calculated by G*Power software, and using FDR correction for multiple testing on three KYN pathway dysregulation values.

Exploratory Research Goal: For the exploratory goal of identifying differences between clinical responders and non-responders, assuming that half of the participants will see clinical improvement (i.e. 20 responders versus 20 non-responders), we are powered to see an effect size of 0.66 between the two groups, as calculated by G*Power software.

Tertiary Endpoint: Change in levels of autoantibodies associated with AITD and celiac disease.

Endpoint Definition: Statistically significant reduction in levels of one or more autoantibodies at 16 weeks as defined by a two-sided, paired Student's t-test.

Method: To determine the impact of Tofacitinib on levels of autoantibodies associated with 1) AITD, i.e. anti-thyroperoxidase (TPO), anti-thyroglobulin (TG), and anti-thyroid stimulating hormone receptor (TSHr), and 2) celiac disease, i.e. anti-tissue transglutaminase (TG) and deamidated gliadin peptide (DGP), a two-sided Student's t-test will be used to compare baseline and 16 weeks of treatment. With 40 participants, we have 80% power to detect an effect size of 0.45 with an FDR corrected p-value less than 0.05, as calculated by G*Power software.

Specific Aim 3. To define the impact of JAK inhibition on immune skin conditions in Down syndrome.

Secondary Endpoint: Change in IGA, DLQI, and/or disease-specific scores.

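### Minor, exploratory only: the individual-cytokine comparison names a KS test without specifying pairing, and the power figures 0.47, 0.66 and 0.68 match calculations other than those described

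*Combined protocol and SAP*

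**What the plan says.** All of this is in section VII, Data Analysis Plan, Specific Aim 2, under goals labelled exploratory.

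- **Individual cytokines.** The test is described as "using a non-parametric Kolmogorov-Smirnoff (KS) test with 40 participants comparing baseline and 16 weeks of treatment". The power claim is "80% power to detect an effect size of 0.47 with a p-value <0.05, as calculated by G*Power software, using FDR correction" for 15 cytokines. The same paragraph says that 15 or more cytokines are measured and that both blood and skin tapes are covered.
- **Responders versus non-responders.** For the IFN score, half of the participants are assumed to improve ("i.e. 20 responders versus 20 non-responders), we are powered to see an effect size of 0.66 between the two groups"). For cytokines the figures are an "effect size of 0.66 for the composite Cytokine Score and 0.68 for individual cytokines". The kynurenine paragraph repeats the first value: "we are powered to see an effect size of 0.66 between the two groups, as calculated by G*Power software".
- **Status.** The composite Cytokine Score is the endpoint and has a two-sided paired t-test. Section IV.C (Research Methods for Specific Aim 2) uses four cytokines for that score, "with the other cytokines being measured for research purposes".

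**The concern.** Three things do not fit together.

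1. Each cytokine is measured twice in the same person. The standard two-sample KS test compares two independent samples. The document's other use of it is of that kind: 54 people without and 75 with trisomy 21 (Figure 4 legend). The name may have been carried over from there.
2. An effect size of 0.47 is barely above the 0.45 given for a single paired t-test with the same 40 people. That leaves almost no room for a correction over 15 tests.
3. Comparing 20 with 20 independent people normally needs a much larger standardised difference than 0.66.

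At stake is sensitivity to within-person change in individual cytokines, and how null results are read. Section VI (Specific Aim 3) says that responder differences would inform follow-up trials. A reader who trusts 0.66 could take a null comparison as better evidence of no difference than it is.

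**Working it through.** **Inputs.** From section VII: n=40 pairs; effect sizes 0.45, 0.47, 0.66 and 0.68; 20 versus 20; 15 cytokines. Assumed: two-sided 0.05; 80% power for the responder figures, because the text gives no level there; normal data unless stated.

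**Formulas.** Power is the noncentral-t probability beyond the critical value.
- Paired or one-sample: noncentrality = d × √n, df = n − 1.
- Two groups of n: noncentrality = d × √(n/2), df = 2n − 2.
- Rank tests: replace n by n × 3/π (asymptotic relative efficiency for normal data), so 40 becomes 38.20 and 20 becomes 19.10.

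**Step 1: the plan's figures.** The effect size detectable with 80% power is the required noncentrality divided by the root term.

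| Calculation | Arithmetic | Result | Plan |
|---|---|---|---|
| Paired t, n=40 | 2.873/√40 | 0.454 | 0.45 |
| Signed-rank, n=40, unadjusted | 2.877/√38.20 | 0.465 | 0.47 |
| One-sample t, n=20 | 2.954/√20 | 0.660 | 0.66 |
| Signed-rank, n=20 | 2.962/√19.10 | 0.678 | 0.68 |
| Two-sample t, 20 v 20 | 2.875/√10 | 0.909 | – |
| Mann-Whitney, 20 v 20 | 2.879/√9.55 | 0.932 | – |

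The first four agree with the plan after rounding. The last two are the comparison that the text describes.

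**Step 2: responders.** Power for 20 versus 20 is 53.0% (t) and 51.0% (Mann-Whitney) at 0.66, and 55.4% and 53.4% at 0.68. A one-sided t-test would still need 0.80. Unequal splits need more: 0.94 for 15 v 25 and 1.05 for 10 v 30 (t-test).

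**Step 3: FDR over 15 cytokines.** Signed-rank power at 0.47 with 40 pairs is 81% unadjusted. At the strictest Benjamini-Hochberg step (0.05/15 = 0.0033) it is 42%, and 80% power there needs 0.63 (paired t) or 0.65 (signed-rank). Simulated average power per truly changing cytokine, independent cytokines:

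| Truly changing, of 15 | 1 | 3 | 5 | 10 | 15 |
|---|---|---|---|---|---|
| Normal, exact p | 44% | 53% | 60% | 71% | 78% |
| t5, approximate p | 54% | 66% | 72% | 82% | 87% |
| Laplace, approximate p | 59% | 70% | 77% | 86% | 89% |

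With normal-approximation p-values the first normal entry is 42%. A between-cytokine correlation of 0.3 changes the normal row little (44% to 76%). If blood and skin tapes formed one family of about 30 tests, power for a single true change would fall to about 31% (normal data).

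**Step 4: the KS test (illustration only).** The within-person correlation r and the distribution are not given. A paired effect of 0.47 is a raw shift of 0.47 × √(2(1 − r)) standard deviations: 0.66, 0.47, 0.36 and 0.30 for r = 0, 0.5, 0.7 and 0.8. Simulated two-sample KS power with 40 values at each time:

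| r | 0 | 0.5 | 0.7 | 0.8 | Signed-rank, same data |
|---|---|---|---|---|---|
| Normal | 64% | 30% | 11% | 4% | about 81% |
| t5 | 79% | 46% | 21% | 9% | about 89% |
| Laplace | 89% | 65% | 37% | 19% | about 91% |

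With no change and normal data, KS rejects in 3.0%, 0.6%, 0.1% and 0.04% of runs. It is conservative, so it adds no false positives. Section III reports that these markers are stable within a person over a year. That points to a high r, but only qualitatively.

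**The case against.** Several points on the other side carry weight.

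- **The form of KS is not stated.** A reader might infer that the plan definitely discards the pairing. A one-sample KS test on within-person differences would use it, with about 74% power at 0.47 (normal data, known SD). The supportable statement is that pairing is unspecified and that the usual KS ignores it. Neither form gives 80% at 0.47 with normal data.
- **A numerical match does not prove that FDR was ignored.** If all 15 cytokines change, the Benjamini-Hochberg threshold is close to 0.05 and power is about 78% (80% with paired t-tests). Heavier tails give more. The panel was chosen to favour change ("This panel consists of cytokines that are significantly elevated in people with DS, with obvious ties to IFN signaling"). Against that, the plan itself says: "Whereas some of the features dysregulated by T21 may be normalized by Tofacitinib treatment, others may not". So 80% after FDR is attainable, but only under assumptions that the plan does not state.
- **The signed-rank origin is an inference.** The plan's one explicit signed-rank figure (Leiter 3, Specific Aim 4) is 0.32, which is not the normal-data two-sided value. The match at both n=40 and n=20 still makes it the most plausible source.
- **No power level is stated for 0.66 and 0.68.** A reader might infer that the plan promises 80% there. The text says only that the study is powered. The 80% comes from the rest of the section and from the match with n=20 calculations.
- **Consequence is small.** The analyses are exploratory, and the plan says that the responder split is hard to estimate. That stands, and it sets the severity.

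**Conclusion.** The point holds as a minor one. The test for individual cytokines is unsuitable or at least underspecified for same-person data. The 0.47 is not a KS figure, and it reaches about 80% after FDR only if essentially all 15 cytokines change (normal, independent data) or the data are heavier-tailed. The 0.66 and 0.68 do not describe a two-group comparison: if 80% power is meant, the detectable difference is about 0.91 to 0.93, and power at the stated values is 51–55%.

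The responder result assumes normal data, an even split, two-sided 0.05 and no multiplicity adjustment. The post-FDR range also depends on the number of tests and of true changes. The KS power grid rests on assumed correlations and should not carry weight beyond its direction.

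A reader might infer that the trial's efficacy conclusions or size are undermined. The documents do not support that. The Cytokine Score endpoint has its own paired t-test, whose 0.45 reproduces, and no endpoint, success criterion, stopping rule or sample size uses these sentences.

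**What to change.** In section VII, Specific Aim 2:

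1. Name a paired test for individual cytokines: Wilcoxon signed-rank (already used for Leiter 3) or a paired t-test. Keep the FDR correction. If signed-rank was intended all along, correct the name.
2. State 0.47 as the unadjusted signed-rank figure for 40 pairs at 80% power. Give any post-FDR power together with its assumptions: the number of tests, whether skin tapes belong to the same family as blood, the number of cytokines assumed to change, and normal, independent data.
3. In the IFN score, cytokine and kynurenine paragraphs, replace 0.66 and 0.68 by about 0.91 (t-test) or 0.93 (Mann-Whitney) for 20 versus 20, two-sided 0.05, 80% power, unadjusted. State the power level.

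The cost is a few sentences, with no extra data or participants. The stated figures become less favourable. Signed-rank does not detect a pure change in spread, so KS could stay as a descriptive supplement.

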Brief Description. The Meso Scale Discovery platform will be used with a custom V-PLEX kit to assess levels of multiple cytokines elevated in people with Down syndrome, including four cytokines that will be used to create a composite Cytokine Score: IP10, TNFa, CRP, IL6. A two-sided, paired Student's t-test will be used to determine the significance of any changes in the Cytokine Score observed.

Name. Change in levels of neurotoxic metabolites in the kynurene pathway.

Type. Tertiary Endpoint.

Time Frame. Baseline and 16 weeks.

Brief Description. Using established mass spectrometry protocols, identification and quantification of kynurene, quinolinic acid, and the kynurene/tryptophan ratio will be performed. A two-sided, paired Student's t-test with FDR correction will be used to determine the significance of any changes observed.

Name. Change in levels of autoantibodies related to AITD.

Type. Tertiary Endpoint.

Time Frame. Baseline and 16 weeks.

Brief Description. Levels of autoantibodies associated with hypothyroidism including anti-thyroperoxidase (TPO), anti-thyroglobulin (TG), and anti-thyroid stimulating hormone receptor (TSHr), will be assessed using established clinical assays. A two-sided, paired Student's t-test with FDR correction will be used to determine the significance of any changes observed.

Name. Change in levels of celiac disease-associated autoantibodies.

Type. Tertiary Endpoint.

Time Frame. Baseline and 16 weeks.

Brief Description. Levels of autoantibodies associated celiac disease including anti-tissue transglutaminase (tTG) and anti-deamidated gliadin peptide (DGP), will be assessed using established clinical assays. A two-sided, paired Student's t-test with FDR correction will be used to determine the significance of any changes observed.

Name. Change in Leiter 3 International Performance Scale scores.

Type. Tertiary Endpoint.

Time Frame. Baseline and 16 weeks.

Brief Description. The Leiter 3 cognitive battery provides a broad non-verbal assessment of cognitive function, including executive function and spatial processing. We will employ the Sustained attention, Nonverbal Stroop Tasks, Forward and Backward Memory and Sequential Order subdomains, to assess inhibitory control, cognitive flexibility, working memory, and spatial processing respectively. An FDR-corrected Wilcoxon signed-rank test (matched pairs) will be used to determine the significance of any changes observed.

Name. Change in CANTAB scores.

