Levels of key autoantibodies associated with AITD and celiac disease. Previous studies defined that ~ 60% of adults with DS carry anti-thyroid antibodies (9-11), and >30% carry autoantibodies linked to celiac disease etiology (18, 52, 114, 115). Thus, as part of our mechanistic investigations, we will measure levels of three key autoantibodies involved in AITD [thyroglobulin (TG), thyroid peroxidase (TPO) and thyroid-stimulating hormone receptor (TSHr)], and two autoantibodies relevant to celiac disease [anti-tissue transglutaminase antibodies (tTG) and deamidated gliadin peptides (DGP) antibodies]. All tests will be performed at the University of Colorado Health Hospital Clinical Laboratory. We define success of this endpoint as statistically significant reduction in levels of one or more autoantibodies at 16 weeks as defined by a two-sided, paired Student's t-test.

Research Methods for Specific Aim 3. To define the impact of JAK inhibition on immune skin conditions in people with Down syndrome.

Given the high prevalence of immune conditions in the DS population and the wealth of data suggesting this could be explained by their obvious hyperactivation of IFN signaling, we propose here to evaluate the impact of 16-week treatment with Tofacitinib on clinical improvement of immune skin conditions. These efforts will be led by a multidisciplinary team of dermatologists with extensive expertise in clinical trials for JAK inhibitors in typical people (Drs. [name], [name], and [name]). Improvement in skin pathology will be the main secondary endpoint of this trial, defined as a statistically significant percentage reduction in average disease scores after 16 weeks of treatment.

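### The autoantibody success definition omits the FDR correction required elsewhere in the plan, and its stated FDR-corrected 80% power is the figure for one uncorrected test with no allowance for antibody-negative participants

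*Combined protocol and SAP*

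**What the plan says.** Section VII (Data Analysis Plan, Specific Aim 2) defines success as "Statistically significant reduction in levels of one or more autoantibodies at 16 weeks as defined by a two-sided, paired Student's t-test". The autoantibody paragraph of Research Methods for Specific Aim 2 repeats the rule in almost the same words: "statistically significant reduction in levels of one or more autoantibodies at 16 weeks as defined by a two-sided, paired Student's t-test". Neither sentence mentions FDR. Three thyroid antibodies (TPO, TG, TSHr) and two celiac antibodies (tTG, DGP) are tested, five in all, and a significant "reduction in levels of one or more autoantibodies at 16 weeks" is enough.

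Two other places do invoke FDR. The Outcome Measures in section IV list the thyroid and celiac antibodies as separate tertiary endpoints and say for each that a "two-sided, paired Student's t-test with FDR correction will be used to determine the significance of any changes observed". The Method under the section VII definition says "With 40 participants, we have 80% power to detect an effect size of 0.45 with an FDR corrected p-value less than 0.05".

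On carriage, Research Methods for Specific Aim 2 cites anti-thyroid antibodies in about 60% of adults with Down syndrome and says that ">30% carry autoantibodies linked to celiac disease etiology". Table 3 schedules every antibody at screening, baseline and week 16 for all participants. No text says how antibody-negative participants enter the test.

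**The concern.** Three things do not fit together.

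- **The deciding sentence lacks the correction.** This is not the plan's general style: the kynurenine definition, also under Specific Aim 2 in section VII, has FDR written into it. As drafted, the same data could meet the endpoint under one sentence and miss it under another. The correction family is also unsettled: the Outcome Measures imply families of three and two, while section VII treats all five as one endpoint.
- **The power figure does not reflect the correction it names.** It has the same sample size, effect size and power as the primary IFN-score endpoint, which is a single test at an unadjusted 0.05.
- **The power figure treats all 40 participants alike**, although the protocol's own carriage figures imply that a sizeable share may be antibody-negative.

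At stake is interpretation. A positive result could rest on an uncorrected rule, and a null result for an antibody could be read as an 80%-powered negative when the power was lower.

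**Working it through.** **Inputs.** From section VII: n = 40 pairs, d = 0.45, two-sided 0.05, five antibodies. From Research Methods for Specific Aim 2: carriage of about 60% (adults, thyroid) and more than 30% (celiac).

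**1. Reproduce the stated power.** Paired t-test, noncentral t with df = n − 1 and noncentrality d√n = 0.45 × √40 = 2.85. At an unadjusted two-sided 0.05, power is 79.3% and the effect detectable with 80% power is 0.454. This matches the plan's 80%.

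**2. Apply FDR.** The strictest Benjamini-Hochberg step for m tests is 0.05/m.

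| Threshold | Power, n = 40, d = 0.45 | Detectable d at 80% |
|---|---|---|
| 0.05 (unadjusted) | 79.3% | 0.454 |
| 0.05/2 = 0.025 (family of 2) | 69.6% | 0.504 |
| 0.05/3 = 0.0167 (family of 3) | 63.6% | 0.531 |
| 0.05/5 = 0.01 (family of 5) | 55.9% | 0.565 |

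Actual Benjamini-Hochberg power lies between the strictest step and the unadjusted value. Simulated with five independent antibodies and d = 0.45 in those that change, power per antibody is about 57% if one changes, 68% if three do and 76% if all five do. None reaches 80%.

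**3. Error rate if the definition is followed literally.** With five independent null tests, 1 − 0.95⁵ = 22.6% for at least one p < 0.05 in either direction. Success requires a reduction, so the relevant figure is 1 − 0.975⁵ = 11.9%. Positive correlation lowers both: at a correlation of 0.5, simulation gives 18.4% and 9.2%. With Benjamini-Hochberg applied and all five null, the either-direction rate is about 5%.

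**4. Antibody-negative participants (illustration).** Assume 0.60 × 40 = 24 carriers for a thyroid antibody and 0.30 × 40 = 12 for a celiac antibody.

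| Carriers | Power at d = 0.45: 0.05 / 0.01 | Detectable d: 0.05 / 0.01 |
|---|---|---|
| 24 | 56.0% / 29.9% | 0.60 / 0.75 |
| 12 | 29.6% / 10.8% | 0.89 / 1.17 |

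If all 40 are analysed instead, let carriers (proportion p) change by 0.45 with SD 1, and let non-carriers have mean change zero with SD s. The effect over all 40 is

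0.45p / √[p(1 + 0.45²) + (1 − p)s² − (0.45p)²].

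- p = 0.6, s = 0: 0.27/√0.6486 = 0.34, power 54%. With s = 1: 0.27/√1.0486 = 0.26, power 37%.
- p = 0.3, s = 0: 0.135/√0.3425 = 0.23, power 30%. With s = 1: 0.135/√1.0425 = 0.13, power 13%.

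These are single-antibody powers at an unadjusted 0.05.

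**5. Power for the endpoint as a whole.** Any one of five suffices, so this is higher. With 24, 24, 24, 12 and 12 carriers, d = 0.45 in all five, and Benjamini-Hochberg over five, simulation gives about 76% if the antibodies are independent, 68% at a correlation of 0.3 and 59% at 0.6. It is lower if fewer antibodies change.

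**The case against.** The strongest reply is that FDR is already prescribed. The Outcome Measures require it for both groups, and the section VII Method names it directly below the definition. That is right, and it limits the point. A reader might infer that the plan has no multiplicity control and carries a 22.6% error rate. The documents do not support that: the defect is a contradiction, and the figure needs a literal reading of the definition, independent tests, and increases counted as successes.

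A reader might also infer that only 24 and 12 participants can show a fall, so that power is 56% and 30% or less. That goes too far as well. The celiac rate is a lower bound. The thyroid rate is for adults, while the trial enrols from age 12. Both are group-level rates from cited literature, so numbers for a single antibody may be higher or lower. The documents do not say that antibody-negative participants have no level to reduce. Single-antibody power also understates power under the any-one-of-five rule.

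A third tempting step is to make a carriers-only test the main analysis. With unchanged, noise-free non-carriers it gains almost nothing: 56% against 54% with 24 carriers, and 29.6% either way with 12. Selecting on the screening value and using Visit 2 as baseline would limit regression to the mean. However, under Combined Screening and Baseline Activities, screening values may serve as baseline with no further draw, so some participants may have no separate Visit 2 value.

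Finally, the Method's "a two-sided Student's t-test will be used to compare baseline and 16 weeks of treatment" drops the word paired. The definition and the Outcome Measures both include it, so this is clerical.

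What stands after all this is the inconsistent definition, the mislabelled power figure, and the silence on antibody-negative participants.

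**Conclusion.** The point holds in a limited form. The two success definitions omit a correction that the plan requires elsewhere; taken literally, with independent tests, the chance of a false reduction is about 12%. The 80% power described as FDR-corrected is the unadjusted value. After correction over five antibodies, power per antibody at d = 0.45 is 55.9% at the strictest step, or about 57% to 76% in simulation with independent antibodies, depending on how many truly change. That conclusion uses only the plan's own n, effect size and number of antibodies. The further loss from antibody-negative participants is real in principle, but its size rests on assumed carrier numbers and on an assumed zero mean change in non-carriers. Because the endpoint is tertiary and mechanistic, and no primary or secondary claim depends on it, severity is low.

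**What to change.** 1. In both definitions (Research Methods for Specific Aim 2 and section VII), add FDR correction and name the family: all five antibodies, or three thyroid and two celiac as the Outcome Measures list them. Use the same family in all three places, and restore the word paired in the section VII Method.
2. Restate the power sentence as 80% power at d = 0.45 for one unadjusted test with 40 pairs, with a detectable d of about 0.45 to 0.57 per antibody after FDR over five.
3. State how antibody-negative participants enter the analysis. Give per-antibody detectable effects over a range of carrier numbers, labelled as an assumption: for example 0.60 (at 0.05) and 0.75 (at 0.01) for 24 carriers, and 0.89 and 1.17 for 12. Note that the any-one-of-five rule has higher power than these single-antibody figures suggest.
4. If an analysis of screening-positive participants is wanted, make it supportive only, and say how those with a combined screening and baseline visit are handled.

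The cost is a few sentences in the plan and no new data. The downside is that the stated power looks less favourable.
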